Evaluating Immunogenicity and Safety Effect on Combined Immune Effect of EV71 Inactivated Vaccine and HepB、MPSV-A、MR、JE-L : A Multi-center Randomized Controlled Trial

Registered classification: prevention of biological products

Clinical stage: stage IV

Program number: EV71-2017-03

Version date: 05 01 2018

Bidding unit:

China Biotechnology Limited by Share Ltd

Wuhan biological products research institute limited liability company

Research unit:

Shandong Center for Disease Control and Prevention

Hunan Center for Disease Control and Prevention

Shaanxi Center for Disease Control and Prevention

Shanxi Center for Disease Control and Prevention

Background

To prevent and control the epidemic of HFMD and related diseases caused by EV71 infection, the development of EV71 vaccine has been developed in many countries or regions. According to the requirements of drug registration approval, we need to evaluate immunogenicity and safety effect on combined immune effect of EV71 inactivated vaccine and other vaccines (HepB、MPSV-A、MR、JE-L).

Method

Four experimental groups (HepB:3+EV71, MPSV-A:1+EV71, MR +EV71, JE-L+EV71) were included in this clinical trial. In addition to the meningococcal vaccine research group, the other three groups were followed up for the 4 times. The initial blood samples were collected, and the first dose vaccine was inoculated at the same time. EV71 second doses of vaccine were inoculated at 30 day, the blood was collected after 30 days of immunization with second doses. 6 months of safety follow-up was carried out in the whole clinical trial after vaccination. The meningococcal vaccine research group increased 1 follow-up after the second dose of MPSV-A vaccine. The index of immunogenicity and safety effect in four experimental groups need to be evaluated.

Study design and participants

The study was conducted in four provinces (Shandong, Shanxi, Shaanxi and Hunan) of China, which contains Haiyang city, Rushan city, Shimen County, Chen Cang District, Qishan County, Taigu County and Qi County. 6/8 months children were

recruited in this study, individuals were randomly assigned to experimental group and control group. Demographic information (age, sex, height and weight) was made and blood samples were collected for each individual in the same way.

Inclusion Criteria

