Exclusion criteria for first needle: (1) the history or family history of anaphylaxis, convulsion, epilepsy, encephalopathy and psychosis; (2) the history of severe inoculation allergies; (3)patients with immunodeficiency and malignant tumors during the treatment period, receiving immunosuppressive therapy (oral steroid) or HIV due to low immunity, or family members have congenital immune disease; (4)Nonspecific immunoglobulin was injected within one month; (5)temperature $> 37.1C^{\circ}$ and infectious diseases; (6)the history of thrombocytopenia or other thrombocytopenia with a definite diagnosis; (7)respiratory disease, acute infection or chronic disease activity period; (8)severe cardiovascular disease (CVD, pulmonary edema, hypertension can not be controlled by drugs to the normal range), liver and kidney disease, and complications of diabetes; (9)infectious, suppurative and allergic dermatosis; (10)other conditions that may affect the evaluation of the trail

Exclusion criteria for follow-up needle: (1)any serious adverse events that have a causal relationship with the inoculation of the upper dose of the vaccine; (2)the abnormality of 4 levels (local, systemic adverse reactions and vital signs) was judged to be related to vaccination; (3)other new

standards of "Exclusion criteria for first needle";(4)other conditions that may affect the evaluation of the trail

Vaccine inoculation and follow-up

Test I (HepB:3+EV71):

Experimental group - 6 month old HepB third dose and EV71 first dose were inoculated at the same time, 7 month old EV71 second dose was inoculated, blood samples from the participants were collected at 8 month old;

Control group 1- 6 month old HepB third dose was inoculated separately, blood samples from the participants were collected after two months;

Control group 2 - 6 month old EV71 first doses was inoculated, 7 month old EV71 second dose was inoculated, blood samples from the participants were collected at 8 month old.

Test II (MPSV-A:1+EV71):

Experimental group - 6 month old MPSV-A first dose and EV71 first dose were inoculated at the same time, 7 month old EV71 second dose was inoculated, 9 month old MPSV-A second dose was inoculated, blood samples from the participants were collected at 10 month old;

Control group 1- 6 month old MPSV-A first dose was inoculated separately, 9 month old MPSV-A second dose was inoculated separately, blood samples from the participants were collected at 10 month old;

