Control group 2 - 6 month old EV71 first doses was inoculated, 7 month old EV71 second dose was inoculated, blood samples from the participants were collected

at 10 month old.

Test III (MR+EV71):

Experimental group - 8 month old MR first dose and EV71 first dose were inoculated at the same time, 9 month old EV71 second dose was inoculated, blood samples from the participants were collected at 10 month old.

Control group 1- 8 month old MR first dose was inoculated separately, blood samples from the participants were collected at 10 month old;

Control group 2 - 8 month old EV71 first doses was inoculated, 9 month old EV71 second dose was inoculated, blood samples from the participants were collected at 10 month old.

Test IV (JE-L+EV71):

Experimental group - 8 month old JE-L first dose and EV71 first dose were inoculated at the same time, 9 month old EV71 second dose was inoculated, blood samples from the participants were collected at 10 month old.

Control group 1- 8 month old JE-L first dose was inoculated separately, blood samples from the participants were collected at 10 month old;

Control group 2 - 8 month old EV71 first doses was inoculated, 9 month old EV71 second dose was inoculated, blood samples from the participants were collected at 10 month old.

EV71 vaccine 0.5ml per dose, Wuhan Biological Products Co., Ltd., Wuhan, Hubei Province, China; 10µg HepB 0.5ml per dose, Wuhan Biological Products Co., Ltd., Wuhan, Hubei Province, China; 30ug MPSV-A 0.5ml per dose, Wuhan Biological

Products Co., Ltd., Wuhan, Hubei Province, China; MR 0.5ml per dose, Beijing Biological Products Co., Ltd., Beijing, China; JE-L 0.5ml per dose, Chengdu Biological Products Co., Ltd., Chengdu, Sichuan Province, China

Immunogenicity end point

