Evaluating Immunogenicity and Safety Effect on Combined Immune Effect of EV71 Inactivated Vaccine and HepB、MPSV-A、MR、JE-L : A Multi-center Randomized Controlled Trial

Registered classification: prevention of biological products

Clinical stage: stage IV

Program number: EV71-2017-03

Version date: 05 01 2018

Bidding unit:

China Biotechnology Limited by Share Ltd

Wuhan biological products research institute limited liability company

Research unit:

Shandong Center for Disease Control and Prevention

Hunan Center for Disease Control and Prevention

Shaanxi Center for Disease Control and Prevention

Shanxi Center for Disease Control and Prevention

Statistical analyses

The quantitative index lists the standard deviation, the median, the maximum and the minimum, and the qualitative index or the grade index list the frequency distribution table. The antibody titers of immunogenicity index should be represented by geometric mean, median, maximum and minimum value and 95% confidence interval. The antibody titer should be analyzed by logarithmic transformation.

A list of the total population, susceptible and non susceptible seroconversion rate and 95% confidence interval, and calculation (test group and control group) rate difference and 95% confidence interval, non-inferiority test; the test group and the control group between the antibody geometric mean (GMT/GMC) compared with the t test after logarithmic transformation P, with less than 0.05 as there were statistically significant differences in the standard.

Arms

Experimental: Combination inoculation group Group I : HepB:3+EV71 Group II : MPSV-A:1+EV71 Group III: MR+EV71 Group IV: JE-L+EV71 Inoculation vaccine made by different techniques(EV71 vaccine 0.5ml per dose, Wuhan Biological Products Co., Ltd., Wuhan, Hubei Province, China; 10 μ g HepB 0.5ml per dose, Wuhan Biological Products Co., Ltd., Wuhan, Hubei Province, China; 30ug MPSV-A 0.5ml per dose, Wuhan Biological Products Co., Ltd., Wuhan, Hubei Province, China; MR 0.5ml per dose, Beijing Biological Products Co., Ltd., Beijing, China; JE-

L 0.5ml per dose, Chengdu Biological Products Co., Ltd., Chengdu, Sichuan Province, China) were given intramuscularly in the deltoid region to participants.

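### The GMT/GMC comparison is an unadjusted log-scale t test at P<0.05, with no planned between-arm ratio and interval and no use of the collected baseline titres

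*SAP*

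**What the plan says.** In the SAP, Statistical analyses, GMT/GMC in the test and control groups are to be "compared with the t test after logarithmic transformation P, with less than 0.05 as there were statistically significant differences in the standard". Neither document plans any other between-arm titre analysis. The same sentence treats rates more fully, with a "rate difference and 95% confidence interval, non-inferiority test".

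Titres do get an interval as a summary, being "represented by geometric mean, median, maximum and minimum value and 95% confidence interval". Listed beside the median and extremes, this reads as a per-arm description and not as a contrast between arms. The SAP's Primary Outcome Measure lists titre only as a distribution before and after immunisation, and attaches the non-inferiority test to the positive rate.

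Baseline blood is available. The Protocol, Method, says "The initial blood samples were collected, and the first dose vaccine was inoculated at the same time". The Protocol, Immunogenicity end point, uses pre-vaccination values to define response. The SAP also splits rates, apparently by baseline status: "A list of the total population, susceptible and non susceptible seroconversion rate". The GMT/GMC comparison makes no use of baseline.

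The Protocol's schedules for Tests I to IV give one post-vaccination bleed per arm. In Test I, for example, "7 month old EV71 second dose was inoculated, blood samples from the participants were collected at 8 month old"; in Tests III and IV, "9 month old EV71 second dose was inoculated, blood samples from the participants were collected at 10 month old".

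**The concern.** The trial asks whether giving EV71 vaccine together with another vaccine changes the antibody response. For titres, the direct answer is a between-arm ratio with its interval, which shows how large a reduction the data still allow. A P value for a difference does not show that. With few children or variable titres, a sizeable fall can be reported simply as not significant.

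The second part is precision. Where baseline titre predicts post-vaccination titre, adjusting for it narrows the interval using data the trial already has. This is plausible for anti-HBs, because group I children enter with two HepB doses (Protocol, Inclusion Criteria). It may be small for EV71, where earlier vaccination and infection are excluded and many baselines may lie below the assay limit.

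**Working it through.** **Inputs.** The documents give no SD, arm size, baseline-outcome correlation (rho) or share of baselines below the assay limit, and no figure of their own to reproduce. All inputs below are assumed: SD of log10 titre 0.4, 0.5 or 0.6; 100 children per arm; observed ratio 0.80; rho 0.1 to 0.7; 0%, 50% or 90% of baselines below the limit.

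**Step 1: unadjusted ratio, direct interval.** The limits are ratio ×/÷ 10^(t × SD × √(2/n)), with t on 2n−2 degrees of freedom. For n = 100 and SD 0.5: 1.972 × 0.5 × √0.02 = 0.1394, and 10^0.1394 = 1.379. The limits are 0.80/1.379 = 0.580 and 0.80 × 1.379 = 1.103.

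**Step 2: can a reader recover this from the planned summaries?** Each per-arm log half-width is t(n−1) × SD/√n, and the two combine in quadrature. For SD 0.5: 1.984 × 0.05 = 0.0992; × √2 = 0.1403; 10^0.1403 = 1.381.

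| SD (log10) | Direct 95% interval | Derived from per-arm intervals |
|---|---|---|
| 0.4 | 0.619 to 1.034 | 0.618 to 1.036 |
| 0.5 | 0.580 to 1.103 | 0.579 to 1.105 |
| 0.6 | 0.544 to 1.176 | 0.543 to 1.179 |

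At 50 per arm the bounds differ by at most 0.01. The unadjusted ratio can therefore be recovered closely, and its absence is a reporting gap.

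**Step 3: what a non-significant P can hide.** At 100 per arm, P exceeds 0.05 for any observed reduction down to a ratio of 10^(−half-width): about 0.77, 0.73 and 0.68 for SD 0.4, 0.5 and 0.6. For SD 0.5 this is 1/1.379 = 0.73.

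**Step 4: gain from baseline adjustment.** Below-limit baselines take a fixed substituted value plus an indicator. Assuming a normal latent baseline and a linear relation, the variance relative to the t test is 1 − rho² × (1 − p × Var(Z | Z<c)). Here p is the share below the limit and c the p-quantile of the standard normal. The bracket is 1.000, 0.818 and 0.359 at p = 0%, 50% and 90%. At rho 0.5 and p = 50%, for example, 1 − 0.25 × 0.818 = 0.80.

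| Share below limit | rho 0.1 | rho 0.3 | rho 0.5 | rho 0.7 |
|---|---|---|---|---|
| 0% | 0.99 | 0.91 | 0.75 | 0.51 |
| 50% | 0.99 | 0.93 | 0.80 | 0.60 |
| 90% | 1.00 | 0.97 | 0.91 | 0.82 |

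Simulating 8,000 trials per setting (100 per arm, SD 0.5) gave 0.995/0.909/0.761/0.512, 1.004/0.939/0.801/0.601 and 1.007/0.974/0.926/0.839. The formula is slightly favourable at 90% below, by less than 0.02. Type I error was 4.8% to 5.3% for the t test and 4.7% to 5.4% for the adjusted model, so both are valid.

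**Step 5: effect on the interval** at 100 per arm, SD 0.5, rho 0.5, holding the observed ratio at 0.80. The log half-width 0.1394 is multiplied by the square root of the variance factor. The equivalent unadjusted arm size is 100 divided by that factor.

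| Analysis | 95% interval | Equivalent n per arm |
|---|---|---|
| Unadjusted | 0.580 to 1.103 | 100 |
| Adjusted, none below limit | 0.606 to 1.056 | 100/0.75 = 133 |
| Adjusted, 50% below | 0.601 to 1.065 | 100/0.7955 = 126 |
| Adjusted, 90% below | 0.589 to 1.087 | 100/0.910 = 110 |

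**The case against.** The best defence is that nothing here is wrong. The t test is valid and makes no claim of non-inferiority on titre. The formal conclusion rests on the rates, which do have a difference, an interval and a non-inferiority test. A ratio follows by back-transformation, and a terse SAP need not list routine output. That stands as an argument against calling this an error. It does not supply a pre-specified estimate, and the planned summaries cannot yield the adjusted ratio, because they do not carry the within-child correlation of baseline and post-vaccination titre.

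A second objection is that the documents support a useful correlation for only one of about nine comparisons. Only HepB has documented earlier doses, EV71 history is excluded, and MPSV-A, MR and JE-L start with a first dose. This is fair. The gain may be small for the first-dose antigens as well as for EV71, and rho 0.5 with every baseline measurable is not a forecast. The ratio and interval are worth having whatever rho is.

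A third objection concerns timing. The Test II schedule bleeds all three arms at 10 months, about three months after the second EV71 dose, whereas the Protocol's Method section speaks of 30 days after second doses. Those passages need reconciling. The schedule still gives one common bleed per arm, so the comparison within the test is defined. Those schedules also list no baseline bleed. Its collection rests on the Method section and is implied by the response definitions.

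**Conclusion.** The concern holds. The plan has no between-arm GMT/GMC ratio with an interval, and its titre comparison ignores baseline values that the trial collects. The unadjusted part is a reporting gap that costs nothing to close. The adjusted part is a possible gain in precision: under the assumed inputs, from nothing useful at rho 0.1 to a variance about half that of the t test at rho 0.7 with every baseline measurable. The actual gain in this trial cannot be computed from the documents. This is a worthwhile improvement and does not invalidate the planned test.

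**What to change.** In the SAP, Statistical analyses, specify for each antigen in each test:

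- Analyse log10 titre or concentration at the single scheduled post-vaccination bleed by analysis of covariance, with arm and log10 baseline value as terms.
- Compare the combined group with control group 1 for the co-administered antigen, and with control group 2 for EV71.
- Fix a rule for baselines below the assay limit before outcome data are examined, for example a set substituted value plus a below-limit indicator. If all baselines are below the limit, the model reduces to the t test.
- Include centre only where that test ran at more than one site. The Protocol names the study area, "which contains Haiyang city, Rushan city, Shimen County, Chen Cang District, Qishan County, Taigu County and Qi County", but does not say which test ran where.
- Report the adjusted GMT/GMC ratio with a two-sided 95% confidence interval. Keep the unadjusted t test, with its own ratio and interval, as supporting analysis.

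The cost is SAP wording and about nine standard models: EV71 in four tests, plus HepB, MPSV-A, measles, rubella and JE (4 + 5 = 9). No new data, visits or blood are needed. The downsides are slightly more analysis work, one rule to settle in advance, and little gain where baseline barely predicts outcome or is mostly below the limit.
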